This is a pilot study designed to produce the data necessary for future larger studies. No data are currently available to guide sample size calculations.

OVERALL EXPERIMENTAL DESIGN The collection of samples and performance of procedures for Substudies A, B and C will typically be performed as indicated below**. Also, V1 may be combined with V0 if subject arrived fasting.

The collection of samples and performance of procedures for Substudy D will typically be performed as indicated in Table 2 on the following page.. However, at the discretion of the PI, some collections may be done at a visit before or after the one shown.

Table 1. Substudy A Rapamycin Only study visits 0, 1, 7-10; **Substudy B ACA+RAPA** study visits 0-10; **Substudy C ACA Only** study visits 0- 6 (as summarized in table below). **TABLE 1 DOES NOT APPLY TO SUBSTUDY D****

Visit number	V0	V1	V2	V3	1V4	1.5V5	2V6	3V7	4V8	5V9	6V10
Visit goal	Consent	Screening	Pre-ACA	ACA – 1 month	ACA – 6-7 wks	ACA ends	Post ACA2 month	termination	7 day RAPA	6 wks RAPA Safety	Imm
Study Phase	A,B,C	A,B,C	B,C	B,C	B,C	B,C	B,C	A,B	A,B	A,B	A,B
Week number (of phase) (time variable between visits 3 and 4)			0	4	6-7	48	12	0 (for RAPA)	1	6	8
Timing (days) – range				25-35 days after V2	38-45 days after V2	50-70 days after V2	25-35 days after V5	25-35 days after visit 2	6-9 days after V7	40-45 days after V7	13-15 days after v9
PROCEDURES											
Consent form	X			X							
EKG		X		X							
Physical exam & history; Safety measures: AE's and problems		X	X	X	X	X	X	X	X	X	X
Clinical blood tests, include:				X			X	X	X	X	X
Complete blood count		X	#			X	X	#	X	X	X
Metabolic profile		X	#			X	X	#	X	X	X
Fasting blood sugar; HbA1c		X	#			X	X	#	X	X	X
Fasting lipid profile		X	#			X	X	#	X	X	X
Urinalysis								x			x
OGTT		X			X		X		x	X	
Acarbose treatment begins			X		X						
Acarbose treatment ends						X	X				
RAPA or placebo begins								X	X		
SF-36 questionnaire			X		X	X	X	X	X		X
RAPA levels									X	X	X
Blood draw for lab, includes:				X			X	X	X		X
Cytokine profiles			X	X		X	X	X	X	X	X
Blood cell subsets by flow			X	X		X	X	X	X	X	X
T cell subsets			X	X		X	X	X	X	X	X
T cell proliferation to mitogen			X		X	X	X	X	X	X	X
Collect feces			X		X	X	X	X	X	X	X
Constipation Assessment			X	X	X	X	X	X	X	X	X
Immunizations: flu vaccine										X	X
T cell prolif to flu antigens									X	X	X
Antibody to flu antigens									X	X	X
Hand grip and 40 ft walk test*			X	X		X	X	X	X	X	X
Cognitive tests: EXIT/SLUMS and/or TAPS*			X	X		X	X	X	X		X
GDS (Geriatr Depression Scale)*			X	X		X	X	X	X		X
CLOX Assessment (cognitive assessment)*		X		X							
PET/MRI								0	0		0

Notes: X=scheduled procedure; O=optional procedure (if funding found and subject consents) *May be done over Visit 0 and Visit 1; #=procedure performed if > 2 weeks from prior measure at V1

Table 2. VISIT SCHEDULE: Sub-study D. Rapamycin Alone – Cardiovascular Effects

VISIT NUMBER	V1	V2	FU1	V3	FU2	V4
Visit goal	Consent/ screen (fasting)	Pre-drug (not fasting)	Phone follow up*	4 wks RAPA	Phone follow up*	8 wks RAPA
Week number		0	1	4		8
PROCEDURES	2-2.5h	3-3.5		2.5-3		4
Consent form and CLOX>10	✓					
SAFETY/AEs/METABOLIC						
Physical exam	✓	✓		✓		✓
ECG	✓					✓
Self reported Adverse Events (AEs)	✓	✓	✓	✓	✓	✓
CBC (blood cell counts)	✓			✓		✓
Fasting blood sugar/CMP	✓			✓		✓
Fasting lipids	✓					✓
HbA1c	✓					✓
Urinalysis	✓					✓
IMMUNE FUNCTION						
Serum for cytokine profiles	✓			✓		✓
Flow cytometry: T cell subsets	✓			✓		✓
T cell activation potential	✓			✓		✓
RAPAMYCIN LEVEL						✓
Meal/snack	✓					✓
COGNITIVE FUNCTION						
Geriatric depression scale		✓				✓
EXIT, SLUMS, TAPS		✓				✓
VR-36 QOL		✓				✓
PHYSICAL FUNCTION						
Hand grip and 40 foot walk		✓		✓		✓
Garmin VivoFit3 Activity Monitor	DISPENSE	BRING*		BRING*		BRING*
DISPENSE STUDY MED		✓		✓		
VASCULAR FUNCTION						
Aortic Pulse Wave Velocity (PWV)	✓**	✓**		✓		✓
Arteriolar Endothelial Function (LDF)	✓**	✓**		✓		✓
CARDIAC/CEREBRAL BLOOD FLOW FUNCTION						
MRI		✓				✓
Schedule MRI - Date						

*Telephone follow up of subjects to assess tolerability and or adverse reactions to RAPA will be conducted at least once between V2 and V3. If tolerating well after 1-2 weeks of RAPA treatment without side effects, no further calls may be necessary. If side effects are reported at any time during RAPA administration, the investigator may choose to modify dosing, if appropriate, and follow by phone on a weekly basis until resolved.

BRING* – At Visits 2, 3 and 4, subjects will bring their Garmin VivoFit3 Activity Monitor so that activity data can be downloaded to a protected server with adequate storage and backup.

**Depending on availability of subjects, shared lab equipment and personnel resources, the vascular function assessments for baseline measurements may be scheduled and performed at Visit 1 OR Visit 2. This allows flexibility and promotes protocol compliance.

Item 7

Risks Section. Risks are described in detail in the Step 2-Institutional Form.

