To investigate ACA as a potential anti-aging therapy for use in humans, we propose a pilot study of ACA in elderly subjects. Our goals are to: i) obtain preliminary data to better estimate power for a larger trial, ii) establish a safe dosing strategy for ACA in non-diabetic elderly humans, iii) determine whether positive ACA outcomes seen in diabetics (i.e., improved endothelial function) are also seen in older non-diabetic subjects, iv) assess whether ACA can reverse age-associated deficits in cognition, physical function, and immunity, and v) determine whether ACA alters the gut microbiome as such changes could impact longevity and immune competence. For ACA, such a translation into geriatric medicine would be relatively straight-forward as it is FDA approved with a low incidence of side effects.

Our current understanding of ACA’s effects primarily derives from patient-based trials in diabetics that report reductions in weight, improved cardiovascular function, and other health benefits. Only a few trials of ACA have been done in non-diabetics and these report beneficial weight reductions. In elderly diabetics (average age \approx 70) ACA was found to be safe and moderately effective in reducing hyper-glycemia. These elderly patients experienced ACA side effects similar to younger groups: primarily flatulence. We propose to assess ACA safety and potential anti-aging benefits in elderly non-diabetics.

Our early preliminary data demonstrate that RAPA at 1 mg/day is well tolerated by elderly humans and hypothesized adverse events (diabetes, immunosuppression, etc.) have not been observed. While these results indicate that RAPA use in healthy elderly persons is not problematic, we have found suggestions of improved cognitive, immune, and physical function. *This leads us to seek objectively measurable outcomes likely to show RAPA benefit. We have concluded that the cardiovascular parameters of aortic compliance and endothelial function answer our quest.*

SubStudy D - Background and Significance – Rapamycin Alone – Cardiovascular Effects

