Subjects will be recruited from the VA Geriatrics Clinics, posted study flyers in community-based private practice offices or senior centers, UT Health Find A Study website, and or newspaper advertisements. Interested candidates will be directed to contact the Barshop Clinical Research Call Center at [contact]. Potential candidates may be contacted by phone from the study team for phone screening after verbal consent is provided. Once the study team establishes contact with a potential candidate who then understands the basics of the study and if desired, interested subjects may receive a copy of the informed consent form by US Postal Service for review prior to the screening appointment. (Email to VA subjects is prohibited.)

Aim D-1. Test whether RAPA increases aortic compliance in elderly subjects. Aortic pulse wave velocity (PWV) will be measured before and during 8 weeks of RAPA administration. Applanation tonometry will be used to

record peripheral waveforms from the carotid and femoral arteries simultaneously with electrocardiogram (ECG) recording to measure PWV. Typically carotid and femoral recordings are performed on the right side of the body, but if necessary may be done on the left.

Aim D-2 Test whether RAPA improves endothelial function in elderly subjects. NO-dependent endothelial function will be measured by monitoring the cutaneous arteriolar vasodilation with laser-Doppler flowmetry (LDF) in response to local warming of the skin from 34°C to 39°C and 42°C. Measurements will be made before, during, and at the end of 8 weeks of RAPA (Table 2).

Aim D-3. Examine whether mTOR inhibition improves diastolic heart function and increases cerebral blood flow in humans.

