Does mTOR inhibition improve diastolic function and/or increase cerebral blood flow in 70-95 year olds? This portion of the project will explore whether mTOR inhibition with RAPA increases cerebral blood flow (CBF) in mouse models of Alzheimer's Disease (AD) and improves cognition (1). Also, rapamycin has been shown to improve diastolic heart function in aging animal models {Chiao, 2016 #2623;Urfer, 2017 #2617}. Our preliminary data in 'oldest old' humans (age 89-93) and a published pilot study (1) suggest similar cognitive effects in humans. We will examine these RAPA effects in older humans (age 70-95). Based on the foregoing observations, we hypothesize that RAPA effects on heart function, the CBF as well as cognitive and physical function are beneficial. We will test our hypothesis in 70-95 year old humans treated with RAPA for 8 weeks by addressing whether systemic RAPA increases CBF in elderly humans. MRI will be used to measure EF, SV, LV volumes, peak LV filling rate, and the E/A wave ratios of flow through the mitral valve. Cardiac data will be normalized to BSA. CBF also will be measured by MRI. Measurements will be made before RAPA is administered, as well as after completion of RAPA administration. Each subject will be his own control in this design.

Aim D-4. Examine whether mTOR inhibition increases levels of activity in humans.

In previous mouse studies, rodents (males) treated with RAPA demonstrated increased physical activity. We hypothesize that RAPA will increase activity levels in humans. Activity data will be collected using a Garmin Vivofit3. We will examine effects on overall activity (time, distance, step count, calories burned, total hours of sleep, periods of movement, and periods of restful sleep) {O'Brien, 2015 #2716;Schrack, 2016 #2715;Šimůnek, 2016 #2714}

Literature Cited

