Approach The advent of next generation DNA sequencing has revolutionized efforts to characterize the endogenous microbiome. In fact, these genomic-based technologies have revealed many new bacterial species that were missed using microbiologic and serologic approaches. The endogenous microbiota plays a critically important role in generating an efficacious immune system and a healthy functioning gut. Of relevance to this proposal, the microbiome also regulates susceptibility to obesity and diabetes. An oral medication, like ACA, will likely target the gut microbiome. Thus, subjects will self-collect feces in sterile containers and deliver it to the clinic at their regular visits. DNA isolation will be performed by the Genomics Core facility on a fee-for-service basis and the samples will be delivered to the Sequencing Core Facility for analysis. The bacterial rDNA in each fecal sample will be amplified using primers from conserved regions of the 16S ribosomal RNA genes. Amplified DNAs are then used to generate a library which is subsequently subjected to deep (next gen) sequencing.

Expected Results For humans, there have been many reports documenting the bacterial species that dominate in older vs. young individuals (24). Given the ages of our subjects, we would expect to see a profile more similar to the “old” profile. It would be most exciting if ACA were to alter the microbiome, making it more “youthful”.

Sub-study D Rapamycin Alone – Cardiovascular Effects

For Aims D-1, D-2, D-3, and D-4:

Intervention with RAPA will begin at the end of Visit 2 once all screening and baseline measurements have been collected. Subjects will self-administer RAPA once daily for a period of 8 weeks (56 doses) and there will be no placebo group in this Sub-study. We will screen 12 MALE subjects to complete 6. No females will be enrolled in this pilot substudy.

Clinical assessment: See also Sub-study A (except without OGTT). In substudies A, B and C, no detrimental diabetogenic effects of RAPA were found, i.e. OGTT, FBS, HbA1c were unaltered by RAPA.

If subjects have previously undergone all or part of screening labs/tests within the past 4 months, the data may be accepted for eligibility determination without screening labs or procedures having to be repeated.

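### Sub-study D compares each man with himself in an open single arm, and no step hides the visit from whoever derives the PWV, LDF and MRI values

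*Combined protocol and SAP*

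**What the plan says.** **Design.** Item 6 (Sub-study D) states "there will be no placebo group in this Sub-study" and "We will screen 12 MALE subjects to complete 6". Under Aim D-3, Item 4 adds "Each subject will be his own control in this design".

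**Motive.** The Item 3 lead-in to Sub-study D says "This leads us to seek objectively measurable outcomes likely to show RAPA benefit", then "We have concluded that the cardiovascular parameters of aortic compliance and endothelial function answer our quest". So the appeal to objective measurement concerns PWV and LDF. MRI comes in separately under Aim D-3: "MRI will be used to measure EF, SV, LV volumes, peak LV filling rate, and the E/A wave ratios of flow through the mitral valve", together with cerebral blood flow.

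**Expected direction.** The Expected Results paragraphs of Item 6 predict lower PWV (Aim D-1), higher skin vascular conductance at 39°C (Aim D-2), and better diastolic function and cerebral blood flow (Aim D-3).

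**Timing.** In Table 2, PWV and LDF are measured at baseline (Visit 1 or 2), Visit 3 and Visit 4. MRI is done at Visits 2 and 4.

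**Measurement.** For PWV, Item 6 fixes supine rest, room temperature, fasting and ECG timing, and gives a CV of 8-12%. Item 4, Aim D-1 makes the right side usual but says recording "if necessary may be done on the left". For LDF, Item 6 gives the temperature steps, an approximate plateau time and the summary value. For MRI, it lists variables and visits.

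**Not found.** The supplied text has no coded files, random reading order, reader unaware of the visit, or rule for accepting a waveform or choosing an LDF segment.

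**Sample size.** The Data Analysis Plan says "No data are currently available to guide sample size calculations".

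**The concern.** In a before/after comparison, the estimated effect is the mean of follow-up minus baseline. Anything that moves follow-up readings systematically in one direction becomes part of that estimate. In a randomised comparison with masked readers, a shift common to both arms would cancel. Here it cannot.

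Some judgement usually enters these measurements: drawing ventricular contours and flow regions on MRI, accepting or rejecting tonometry waveforms, and deciding where a flow plateau begins and ends. A reader who knows the visit and the predicted direction could make these choices lean one way without intending to.

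What is at stake is the quality of the pilot's product. The plan says the data are to support larger studies. An effect estimate inflated by reading would mislead that planning, and the confidence interval would give no sign of it.

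**Working it through.** **Is the visit hidden anywhere?** I set the design and measurement sections side by side.

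| Measure | Visits | Direction predicted | Standardisation described | Visit hidden from reader |
|---|---|---|---|---|
| PWV | Baseline, V3, V4 | Lower | Rest, temperature, fasting, ECG timing | Not stated |
| LDF | Baseline, V3, V4 | Higher | Temperature steps, approximate plateau time, averaged maxima | Not stated |
| MRI | V2, V4 | Improved | Variables listed | Not stated |

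The described controls reduce noise and some discretion. None of them conceals the visit.

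**Effect of a shift on the estimate.** If every post-treatment reading moves by b per cent of baseline, the mean change moves by b. The shift does not shrink with more subjects.

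**How often this would mislead, for PWV.** The plan gives no alpha, power or target effect for Sub-study D, so there is no figure of its own to reproduce. This is an illustration.

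Inputs:
- From the plan: n = 6 completers and PWV CV = 8-12%.
- Assumed: paired t-test, two-sided alpha 0.05, SD of change = √2 × CV (no true variation between men in their change), no drug effect, and shift b of 3%, 5% or 10%.

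Formulas:
- Standard error: SE = √2 × CV / √6
- Smallest significant mean change: t(0.975; 5 df) × SE = 2.571 × SE
- Chance of a significant favourable result: P(T > 2.571), where T is noncentral t with 5 df and noncentrality b / SE

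For CV 8%: SD = 1.414 × 8 = 11.31; SE = 11.31 / 2.449 = 4.62; threshold = 2.571 × 4.62 = 11.9%. With b = 5, the noncentrality is 5 / 4.62 = 1.08 and the chance is 14.2%.

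| CV | SE | Threshold | b = 0 | b = 3% | b = 5% | b = 10% |
|---|---|---|---|---|---|---|
| 8% | 4.62 | 11.9% | 2.5% | 7.7% | 14.2% | 41.8% |
| 10% | 5.77 | 14.8% | 2.5% | 6.3% | 10.6% | 29.1% |
| 12% | 6.93 | 17.8% | 2.5% | 5.5% | 8.6% | 21.7% |

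The plan gives no variability for LDF or MRI, so the same calculation cannot be made for them.

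**The case against.** The strongest reply is that the bias is only a possibility and the study is a six-man pilot. The plan does not say who reads the files or in what order. My account of MRI contouring and waveform selection is general knowledge, not taken from the plan. The PWV and LDF procedures are standardised, which narrows the room for expectation. The shift sizes have no source, and with six men a significant PWV result needs a mean change of 11.9-17.8%, so a 3-5% shift would seldom produce one by itself. All of this stands. It limits the size of the claim but does not close the gap, because standardisation is not masking and the estimate absorbs the shift whether or not p falls below 0.05.

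Four stronger readings are tempting, and the documents do not support them:
- *All three modalities are presented as objective.* Item 3 attaches that description to aortic compliance and endothelial function only.
- *PWV switches side between visits.* Item 4 permits the left side if needed. It does not say that a man's side changes. A change of side would in any case add noise and not expectation bias.
- *Masked reading is the only safeguard left without a placebo group.* Repeat baseline measurements or an off-drug reassessment also need no placebo; Sub-studies B and C already plan a visit after acarbose is stopped.
- *Masked reading would make the change attributable to rapamycin.* Regression to the mean, time trends and placebo response would remain, and they may be larger.

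It is also true that staff recording PWV and LDF live will know the visit, and that an analyst handling so few men may recognise some files.

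**Conclusion.** The concern holds in this form: an open, single-arm before/after comparison, with a favourable direction stated for PWV, LDF and MRI, has no step that hides the visit from whoever derives the values. The documents show that directional reading is possible. They do not show that it will occur.

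Any shift passes in full into the mean change. Under the stated assumptions, a 5% PWV shift takes the chance of a falsely favourable significant result from 2.5% to 8.6-14.2%, and a 3% shift takes it to 5.5-7.7%. If men truly differ in their change, the SD is larger and these chances are smaller, but the bias in the mean is the same. Exposure for LDF and MRI cannot be sized from the documents.

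The change is worth making because the estimates are meant to inform later studies and the protection is cheap. It is not a reason to hold up the sub-study.

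**What to change.** - Store the MRI files (V2, V4) and the PWV and LDF files (baseline, V3, V4) under random codes that conceal subject and visit. An existing team member who does no reading holds the key.
- Before any endpoint reading, write down the rules for accepting waveforms and images and for choosing LDF segments.
- After the last V4, have the usual analyst measure all files in random order. Lock the values, then break the code.
- Keep safety reads immediate and separate from endpoint reads.
- Record each man's PWV on his baseline side where feasible, and log any change of side.
- State in the analysis plan that masking covers offline reading only, and that regression to the mean, time and placebo effects are not removed.
- Reconcile the Aim D-1 Expected Results in Item 6, which still predict an outcome for a placebo group, with the statement that Sub-study D has none.

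**Cost.** Endpoint readings wait until the last visit, and someone must code and hold the files. With 6 completers that is 6 × (2 MRI + 3 PWV + 3 LDF) = 48 sessions' files. No new reader, visit or procedure is needed.

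### In Sub-study D, screening labs up to 4 months old can replace the Visit 1 panel, the only pre-drug lab panel in Table 2, so the safety and metabolic baseline can be months old

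*Combined protocol and SAP*

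**What the plan says.** All references are to the combined protocol and SAP.

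- **Waiver.** Item 6, Sub-study D, under the clinical assessment paragraph: prior screening labs or tests done "within the past 4 months, the data may be accepted for eligibility determination without screening labs or procedures having to be repeated". Sub-study A carries the same sentence.
- **Start of drug.** Same section: "Intervention with RAPA will begin at the end of Visit 2 once all screening and baseline measurements have been collected".
- **Control.** Same section: "there will be no placebo group in this Sub-study". Under Aim D-3 in Item 4: "Each subject will be his own control in this design".
- **Lab schedule.** Table 2 ticks CBC and the row "Fasting blood sugar/CMP" at V1, V3 (4 weeks) and V4 (8 weeks). It ticks fasting lipids, HbA1c and urinalysis at V1 and V4. None of these is ticked at V2, which is labelled a non-fasting visit.
- **Repeat rule elsewhere.** The Table 1 notes define the # mark as "procedure performed if > 2 weeks from prior measure at V1". The mark stands against CBC, metabolic profile, fasting glucose/HbA1c and lipids at V2 (pre-acarbose) and V7 (start of rapamycin or placebo). Table 1 is expressly not applicable to Sub-study D, and Table 2 has no similar note.
- **Cross-reference.** The Sub-study D clinical assessment paragraph refers the reader to Sub-study A, apart from the OGTT. The Sub-study A text includes blood chemistry among the assessments made at every visit.

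**The concern.** Sub-study D is uncontrolled, so a lab change can be judged only against the subject's own pre-drug value. If that value was obtained months before dosing, whatever happened in between is mixed with the change on drug, and no comparison group is available to separate the two.

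The labs are more than an entry screen. The abstract (Item 2) lists blood chemistry among the tests used in Sub-study D to detect drug-related change and to confirm safe delivery. Item 6 (Methods for Sub-study A & B) lists seven adverse reactions to rapamycin and related agents used alone. Four of them (hyperlipidemia, hyperglycemia, thrombocytopenia, anemia) are detected by these panels. Sub-study D also omits the OGTT, so fasting glucose and HbA1c carry the metabolic question. With 6 planned completers, one subject with an old baseline is 1/6, about 17%, of the data.

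**Working it through.** The plan states no figure for the age of baseline labs and no sample size calculation, so there is nothing to reproduce. The check sets the waiver against the schedule and works out the intervals.

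**Inputs**
- Look-back window: 4 months, taken as 120 days (assumption: 30-day months). Item 6, Sub-study D.
- V1 to V2: about 2 weeks, 14 days. Aim D-4, the activity-monitor run-in from consent to baseline.
- First dose: end of V2. Item 6, Sub-study D.
- First dose to V4: 8 weeks, 56 days. Item 6 and Table 2.
- Start of the look-back: not defined. It could run back from V1 or from first dose, so both are shown.

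**Formulas**
- Interval to V4 = lab age at first dose + 56.
- Pre-drug share = lab age at first dose / interval to V4.

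| Case | Lab age at first dose | Interval to V4 | Pre-drug share |
|---|---|---|---|
| Drawn at V1 as scheduled | 14 days | 14 + 56 = 70 days | 14/70 = 20% |
| Waiver, counted back from first dose | 120 days | 120 + 56 = 176 days | 120/176 = 68% |
| Waiver, counted back from V1 | 120 + 14 = 134 days | 134 + 56 = 190 days | 134/190 = 71% |

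Calendar months give the same shares. 4 × 365.25/12/7 = 17.4 weeks, or 19.4 weeks with the run-in. The shares are 17.4/25.4 = 68% and 19.4/27.4 = 71%.

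**What the shares mean.** They are proportions of calendar time, not bias in a lab value. As an illustration, suppose a lab drifts at a constant rate unrelated to drug. The drift included in the week-8 change is then proportional to the whole interval, so it grows by 176/70 = 2.5 to 190/70 = 2.7 times under the waiver. If there is no drift, it stays at zero. The documents give no drift rate, variance or within-subject correlation for these labs, so the analysis cannot go further.

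**Which measures are exposed**
- CBC, lipids, HbA1c, urinalysis: V1 is the only scheduled pre-drug draw, so they are exposed.
- Fasting glucose/CMP: exposed on Table 2, possibly not on the cross-reference to Sub-study A.
- Grip, walk, cognition, MRI: measured at V2, not exposed.
- PWV and LDF: baseline taken at V1 or V2 as aim-specific measurements, not exposed.
- Activity: recorded during the run-in, not exposed.
- Cytokines and T cell measures: pre-drug only at V1, but the text does not clearly class them as screening labs, so no claim is made.

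**The case against.** The strongest reply has five parts.

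1. **The waiver is about eligibility.** It does not call the old result a baseline, and the start-of-drug sentence names screening and baseline measurements separately. This is correct as to wording. But the waiver also removes the repeat, and Table 2 schedules no other pre-drug draw of these labs. Unless someone adds a draw, the old value is the only one available.
2. **Chemistry is covered at every visit.** A reader might infer from Table 2 that no pre-drug draw other than V1 is planned for any lab. The documents do not support that for chemistry. The cross-reference to Sub-study A can be read as calling for chemistry at V2. It does not clearly reach CBC, lipids, HbA1c or urinalysis, and it conflicts with Table 2, where V2 has no lab ticked and is non-fasting.
3. **Collections may be moved.** The overall design text lets the PI shift some collections to an adjacent visit. That is permission, not a required pre-drug draw.
4. **The aims are untouched.** A reader might extend the point to the whole self-controlled design. That does not stand: the own-control statement sits under Aim D-3, and Aims D-1 to D-4 have their own pre-drug measurements. Table 2 groups the labs under safety and metabolic items, and no baseline-to-week-8 lab analysis is specified.
5. **Stable subjects, optional waiver.** Chronic disease must be clinically stable at entry, and how often the waiver would be used is unknown. Both limit the likely effect without removing it.

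**Conclusion.** The concern holds for the safety and metabolic labs in Sub-study D. Followed as written, the plan can leave CBC, lipids, HbA1c and urinalysis with a single pre-drug value about 120 to 134 days old at first dose, against about 14 days as scheduled. The same may apply to glucose/CMP, depending on how the text and Table 2 are reconciled.

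This rests on a 30-day month, a run-in of about 2 weeks, and full use of the look-back window. The upper end applies only if the window runs back from V1. It describes what is permitted, not what will happen to each subject. A reader might take 71% as the share of an observed change that is spurious, but it is only the upper end of a share of time. Nor do the documents say that old results will be analysed as baseline; they leave no other scheduled value.

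The point is worth correcting before enrolment, because a missed pre-drug value cannot be recovered after dosing. It does not threaten the vascular, MRI or activity aims.

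**What to change.** In Item 6, Sub-study D and in Table 2:

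- State that prior results may decide eligibility but do not replace the V1 panel.
- Draw the V1 fasting panel (CBC, fasting glucose/CMP, lipids, HbA1c, urinalysis) for every Sub-study D subject, and name it as the baseline. V1 is already a fasting visit with blood scheduled for the immune tests.
- Add a maximum age of the baseline panel at first dose, with a repeat only if V2 slips beyond it. Do not copy the Table 1 threshold unchanged: 2 weeks falls on the planned V1-to-V2 gap and would trigger repeats in subjects with fresh labs. The limit should leave room for the run-in. Any repeat needs a fasting draw, which V2 is not. Table 1 does not apply its # mark to urinalysis, so including it is a small extension.
- Reconcile Table 2 with the Sub-study A cross-reference on whether chemistry is drawn at V2.

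The cost is one routine panel for each subject who would have used the waiver, and an occasional repeat fasting draw when V2 is delayed. A fresh baseline shortens the pre-drug interval but does not supply a control group, so change on treatment remains descriptive.
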